Since [name] sperm freezing success in 1953 with a subsequent live birth, collecting and using sperm for insemination in humans was made possible. However, it would be more than a decade before it became legally possible as it was initially ruled as contrary to public policy and good morals. In the 1960s and 70s, sperm selection and washing techniques led to Intrauterine insemination (IUI) which placed the sperm even further into the woman's body by putting it directly into the uterus. By the 1970s sperm banks in the US became popular. Also in the 1970s, Steptoe and Edwards introduced the world to In-Vitro Fertilization (IVF). More recently, techniques such as intratubal insemination, and intraperitoneal insemination have been added to the available conception methods. During the last decades the popularity of Intrauterine Insemination (IUI) increased because it was safer, painless, and more cost-effective. Additionally, more information has become available about sperm selection techniques and now there is a greater understanding of many of the causes of infertility.

The most popular method of insemination is to use the husband's sperm (Artificial Insemination by Homologous or Husband (AIH)). In some cases anonymous donor sperm is used. Intracervical (ICI) or intravaginal insemination (IVI) are terms used interchangeably to describe the insemination technique colloquially known as the "turkey baster method". This method consists of placing the semen into the vagina at or near the cervix. In the United States, IUI is the most frequently doctor assisted technique. Some researchers have examined the success rates of each technique. ICI/IVI has been found to have a per cycle pregnancy rate of 10-15% while IUI has been found to be slightly higher up to 10-35%. Meanwhile techniques such as IVF can be as high as 31% in people under 35 years of age and as low as 3% for those above 43 according to the CDC.

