3 OBJECTIVES AND ENDPOINTS

OBJECTIVES	ENDPOINTS	JUSTIFICATION FOR ENDPOINTS	PUTATIVE MECHANISMS OF ACTION
Primary			
The primary objective is to understand the outcome of using the at-home intracervical insemination Mosie kit, i.e. pregnancy rate after its use.	The primary endpoints is: Pregnancy Rate after up to 6 cycles. Another primary end point is to understand the rates of pregnancy in people who desire to get pregnant without intercourse (i.e. both single and those in LGBTQ relationships.	The ultimate objective of using the Mosie Kit is to end up pregnant. Thus pregnancy rate is a primary endpoint. Specifically, pregnancy rate in up to 6 (six) cycles will be examined as it is the typical standard timeframe for attempting to get pregnant using IVI or IUI before seeking an alternative method. People who have no known fertility issue who are trying to conceive without intercourse such as those who are in LGBTQ relationships or those who are not in any relationship at all will likely have higher pregnancy rates than those with known fertility issues of female origin. Women in LGBTQ relationships wishing to conceive might also have a higher pregnancy rate than those in heterosexual relationships where infertility might be caused by things like low sperm count, sperm motility issues or erectile dysfunction (ED).	The Mosie Kit is intended to be used to deposit semen at or near the cervix where the sperm will have an increased likelihood of entering the uterus and pairing up with the ovum resulting in a pregnancy. Pregnancy rates increase when sperm reaches the ovum and fertilizes it. In people with no known fertility issues, the Mosie kit deposits the semen where it is able to fertilize the ovum. People without infertility issues who want to get pregnant without sex by using the Mosie Baby are also more likely than people with known fertility issues to get pregnant.

Secondary			

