4.3 Justification for Intervention

This is a retrospective cross-sectional study of existing users of the Mosie Kit. Participants will be recruited via email. Specifically, it is planned that participants will receive up to 5 email invitations to participate in the study, however more emails might be used to recruit sufficient participants.. The email will direct them to the study survey where they will read the consent form and choose to participate in the study. The email will contain a link to the survey. If they elect to participate, they will complete the study survey and submit it online. Participation consists of completing a 10-20 minute survey. This is a one time survey. Since no identifying information will be collected, there will be no possibility of follow up.

There is no intervention. This study merely looks at the past experience of using the Mosie Kit. It is important to know the success rates of pregnancy with at-home insemination kits, and understand the usability and safety as there are individuals and couples using these types of options on a regular basis as a means to get pregnant. For people who suffer from infertility, having this information will help them choose whether ICI is right for them and whether the Mosie Kit should be chosen for this method. Additionally, since age is a factor in pregnancy success and risks increase with age, there is a need to understand the success of at home ICI so recommendations can be made as to whether to use ICI and how long to use it before seeking other methods of conception. This study aims to address some of these issues.

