7.2 Participant Discontinuation/Withdrawal from the Study

Participants may choose to leave the survey at any time without submitting the completed survey. There will be no way to know which participant did not complete the survey or why the survey was not completed. There will be no way to follow up with the participant to request continued participation as the survey will not contain any identifying information.

There will be no replacement participants. Any incomplete surveys will be discarded automatically by the system. They will not be available for use in the final analysis.

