9.1 Statistical Hypotheses and General Statistical Approach

The primary objective is to understand the outcome of using the Mosie kit for Intracervical insemination, i.e. pregnancy rate after its use. Specifically the hypothesis is as follows.

Primary hypothesis 1: Pregnancy rates using the at-home insemination Mosie Kit to deposit semen near or at the cervix (i.e. intracervical insemination) are equivalent or better than traditional in doctor's office intrauterine insemination (IUI). Conversely the null hypothesis is that the pregnancy rates using the at-home insemination Mosie Kit to deposit semen near or at the cervix do not have higher rates of pregnancy than in doctor's office IUI.

Analysis: Comparison of total rates of pregnancy using the Mosie Kit to the 10-20% rate reported for IUI by the American Pregnancy Association.

Primary Hypothesis 2: Pregnancy rates of LGBTQ couples or single women using the Mosie Kit where the female has no know fertility issues will be higher than that of heterosexual couples with a known fertility cause or those that are designated as having an unexplained fertility issue. The alternative hypothesis is that people with no known

fertility issues using the Mosie Kit will have less pregnancies than heterosexual couples with known fertility issues.

Analysis: Rate of pregnancy using the Mosie Kit will be obtained for the following groups: LGBTQ couples where carrying female has no known fertility issues, LGBTQ couples where carrying female has a known fertility issue, Heterosexual people with no known fertility issue, Heterosexual people with a known fertility issue, Single females with no known fertility issue and Single females with a known fertility issue. The rates of each group will be analyzed using descriptive statistics and the aggregate of the 3 groups with fertility issues will be compared with the aggregate of the 3 groups without fertility issues. An ANOVA will be used to compare the differences between groups.

Secondary Hypothesis 1: The participants perceived the Mosie Kit to be easy to use for its intended purpose. The alternative hypothesis is that the participants perceive the Mosie Kit to be difficult to use for its intended purpose.

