10.1.9.1 Data Collection and Management Responsibilities

Google forms will be used to collect this one time survey. The only data quality checks that will be included in the survey will be those that are implemented via the appropriate selection of the type of field in order to ensure the appropriate data is entered into the field and edit checks to ensure all questions are filled in.

The online Google Form and resulting excel sheet will constitute the source data for this study. No external records or information will be combined with the survey data. Only the PI and the Sponsor will have access to download the data.

Data standards will be implemented for the study. Descriptive field names will be used for each field. All data collection is the responsibility of the PI. The PI is responsible for ensuring the accuracy and completeness of the data.

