[figure not shown]
How did you or your partner time your ovulation? (Select all that apply.) *
Count days in cycle
Track vaginal or cervical fluids
Tracking changes in the cervix
Use ovulation predictor kit
Use an app to estimate ovulation
Basal Body Temperature
Wearable device
Did not time ovulation
Did using Mosie result in a pregnancy? *
O Yes
O No
Back Next Page 10 of 20

[figure not shown]
Never submit passwords through Google Forms.

 $This \ content \ is \ neither \ created \ nor \ endorsed \ by \ Google. \ \underline{Report \ Abuse} - \underline{Terms \ of \ Service} - \underline{Privacy \ Policy}$

Google Forms

Page 56

[figure not shown]

Safe process

Enjoyable

	Very Easy	Easy	Neutral	Difficult	Very Difficult
To collect the semen/sperm sample in the cup?	0	0	0	0	0
To draw up the semen/sperm in the syringe?	0	0	0	0	0
Insert the Mosie syringe into the vagina up to the handles?	0	0	0	0	0
To deposit the semen/sperm at or near the cervix using the syringe?	0	0	0	0	0
My overall impression on the ease of use	0	0	0	0	0
					Page 12 of 20
submit passwords to	through Google Fo				

MOSIE-001 © 2020 Mosie Baby Page 59

MOSIE-001 © 2020 Mosie Baby

Page 60

Pulled the syringe plunger back and forth to confirm it was functioning.

My partner washed their hands

Use a sperm friendly-lubricant.

Thawed out donor sperm from sperm bank

Prepared all items and have them handy ready to use.

Washed the penis

that	apply)?*
	Lie down in a comfortable position.
	Relax
	Receive oral sex
	Stimulate clitoris
	Use any vibratory or non-vibratory stimulation device intravaginally
	Have an orgasm
	Other:
	erall, how well were you able to use the Mosie syringe to inseminate yourself our partner? * Very Able
	our partner? *
or y O O O	our partner? * Very Able Able Not Very Able
or y 0 0 0 0	Very Able Able Not Very Able Not Able at All Volume at All Volume at All Volume at All Volume at All Able at All Volume at All Able at All Able at All
or y O O O	Very Able Able Not Very Able Not Able at All Volong did you remain laying down after using the Mosie syringe? * Less than 15 minutes

Willelf best descri	ibes your lying position? *	
On my stomach	n	
On my side		
On my back		
On my back wit	th my hips elevated by a pillow	
Other:		
O No		
O		
What type of sam	ple did you use? *	
What type of sam	ople did you use? * rom a sperm bank (frozen)	
What type of sam	rom a sperm bank (frozen)	

0 2000	thank 50%	
O 51%-	70%	
O 71% -	80%	
O 81%-	90%	
O 90%-	95%	
O 96%-	100%	

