Multiracial o	r Multiethnic	
Black or Afri	can American	
Hispanic or	_atinx	
· White		
Native Amer	ican or Alaska Native	
Native Hawa	iian or other Pacific Islander	
Asian Ameri	can	
Indian Amer	can	
Other		
What is your ap	proximate household income?*	
Choose	•	

Hov	v would you describe yourself? *
0	Woman
0	Man
0	Transgender
0	Non-binary
0	Prefer not to say
0	Other:
0	Single/Not in a relationship LGBTQ Relationship Other:
Are	you married? *
0	Yes

	ID 17 directed you	ır family building	plans? *	
O Yes				
O No				
If yes, pl	ease share how it h	as affected you	r family building	g plans.
Your ansv	ver			
Is there	anything else you w	ould like to sha	re with us?	
Your answ	ver			
	Next			Page 1
Back				, and the second
	asswords through Googl			

Mosie Kit Survey

THANK YOU! We so appreciate you!

Use code WARMHUGS for 15% off your next purchase.

If you did conceive with the Mosie Kit, we'd love to celebrate your joyful news and send you a special baby gift. Email us at [contact] to share your news!

If you're still on your journey to conceive, we are sending you big hugs! We want to help and support you as best we can, no matter the path taken, we are here for you! If you have any questions or if you're interested in sharing your current journey to conceive with the Mosie Community, email us at [contact]. Fingers crossed for you!

Our thanks and best wishes to you! Team Mosie Baby

This content is neither created nor endorsed by Google. Report Abuse - Terms of Service - Privacy Policy

Google Forms

MOSIE-001 © 2020 Mosie Baby Page 79

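### The required pregnancy question has no answer for a result that is not yet known, so a respondent with a pending cycle will most naturally be recorded as not pregnant

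*Combined protocol and SAP*

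**What the plan says.** **The item.** Appendix A asks "Did using Mosie result in a pregnancy", marks it as required, and shows Yes and No as the only options before the page footer. Section 10.1.9.1 plans "edit checks to ensure all questions are filled in", and section 7.2 states "Any incomplete surveys will be discarded automatically by the system". The item therefore cannot be left blank and still reach the database. Section 4.3 adds that "there will be no possibility of follow up".

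**The endpoint and analysis.** Section 3 defines the primary endpoint as "Pregnancy Rate after up to 6 cycles". For Primary Hypothesis 1, section 9.1 plans a "Comparison of total rates of pregnancy using the Mosie Kit to the 10-20% rate reported for IUI by the American Pregnancy Association". Sections 9.1 to 9.4 say nothing about outcomes still unknown on the survey date.

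**Timing.** Section 5.1 requires use in one cycle or more and sets no minimum time since the last insemination. Section 5 limits the date of purchase to 2 to 8 complete months before study start and expects use within a month of purchase. Section 9.3 describes the analysis population by use in that same window. Appendix A has separate cycle sections up to cycle 6.

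**The concern.** A user between an insemination and a readable test has neither a Yes nor a No to report. No is the natural choice, and it is then stored in the same way as a cycle known to have failed. Nothing in the legible form separates the two, and an anonymous one-time survey cannot be corrected later.

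This is a different problem from unequal exposure. Reporting by number of cycles would handle respondents who have tried fewer times. It would not repair a cycle that enters the data as finished when it is not.

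At stake is the estimate of the primary pregnancy rate, which sections 10.1.3 and 10.1.11 intend for publication and possibly for marketing. Every subgroup rate built on the same item is affected too.

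**Working it through.** **Inputs**
- Per-cycle rate p: section 2.2 gives a "per cycle pregnancy rate of 10-15" percent for intracervical insemination.
- Target n = 500 with a half-width of 4.4 points, and minimum n = 384 with 5 points (section 9.2).
- Share of respondents with a pending cycle and no earlier kit pregnancy, f: not in the documents. Assumed range 5-25%.

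**The plan's own precision figures.** The half-width is 1.96 × √(0.25/n).
- n = 500: 1.96 × √(0.25/500) = 4.38 points, matching the stated 4.4.
- n = 384: 1.96 × √(0.25/384) = 5.00 points, matching the stated 5.

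**Who can be pending.** A kit supports two inseminations within one cycle (section 2.3.2). Someone who bought one kit two or more months ago and used it within a month should know the result. Pending results need late use, a repeat purchase or a later cycle. The endpoint covers up to six cycles, and no criterion or legible item limits the time since the last insemination. Such respondents are therefore possible, but their number is unknown.

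**Person-level bias.** Each pending respondent would have become pregnant with probability p but is counted as No. The understatement is f × p.

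| f (assumed) | p = 10% | p = 15% | Pregnancies missed among 500 |
|---|---|---|---|
| 5% | 0.5 points | 0.75 points | 2.5 to 3.75 |
| 10% | 1.0 | 1.5 | 5 to 7.5 |
| 20% | 2.0 | 3.0 | 10 to 15 |
| 25% | 2.5 | 3.75 | 12.5 to 18.75 |

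More surveys do not reduce this.

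**Per-cycle rate, if one were reported.** With m cycles per respondent on average, including the pending one, the observed rate is p × (m − f)/m. The loss is p × f/m. At an assumed m = 3, this runs from 0.10 × 0.05/3 = 0.17 points to 0.15 × 0.25/3 = 1.25 points.

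**Group comparisons.** At a common per-cycle rate the distortion of a difference is (f₁ − f₂) × p. It is zero if the groups have equal pending shares. With 25% against 5% and p = 15%, it is 0.20 × 0.15 = 3.0 points.

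**What a third answer option changes.** Let s be the fraction of pending respondents for whom the pending cycle is their only one. Excluding them turns an observed rate R into R/(1 − f × s). With R = 20% and f = 10%, s = 0 leaves 20%, and s = 1 gives 0.20/0.90 = 22.2%. Respondents with earlier failed cycles stay in the denominator as not pregnant on those cycles. The rule makes the rate refer to completed cycles. It does not recover the f × p pregnancies.

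**The case against.** The design has a lag built in. The two-month minimum since purchase, the expectation of prompt use and the wording of section 9.3 all push towards known outcomes. This stands for promptly used single kits. It does not close the gap, because prompt use is an expectation, and no legible item or analysis rule applies the section 9.3 window to later cycles.

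A reader might infer that pending users are forced to answer No. The documents do not support that. The survey is open for about 30 days, with up to five emails, and can run to 90 days, so a user can wait. A user can also quit, guess Yes or explain in the open comment field. However, the sample emails in Appendix C do not ask anyone to wait for a result, and a comment is optional.

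A reader might also take the closing page, addressed to those "still on your journey to conceive", as proof that the sponsor expects users who are awaiting a test. It is a thank-you message to anyone who has not conceived, including people who have stopped using the kit. It shows only that non-pregnant respondents are foreseen.

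The bias is downward and so works against the sponsor's claim of being equivalent or better. That stands, although the stated objective is also to learn the rate itself.

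Finally, several survey pages are not shown, and Appendix A allows questions to be revised for clarity. An unseen date or current-status item is possible. Even so, section 9 uses no such item to reclassify an answer.

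**Conclusion.** The concern holds as a limited and cheaply corrected weakness of the questionnaire. A pending cycle has no answer of its own and will most naturally be counted as not pregnant, which biases the pregnancy rate downward.

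The size is f × p. Only p comes from the protocol, so the 0.5 to 3.8 points is an illustration over an assumed 5-25% pending and not an estimate. The upper end approaches the planned half-width of 4.4 points, but it needs a quarter of respondents to be pending, which the purchase lag makes less likely.

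The error is conservative for Primary Hypothesis 1. A reader might go on to infer that the subgroup comparisons are distorted. At a common per-cycle rate that follows only if groups differ in the share pending, and the documents give no evidence on this.

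**What to change.** Add a third answer to the item: *No earlier pregnancy; too early to know for the most recent cycle*. Then state in section 9.1:
- In the person-level rate, exclude respondents whose only cycle is pending. Count those with earlier completed cycles on those cycles only.
- In any per-cycle rate, drop the pending cycle.
- Report the number pending, overall and by comparison group.
- Repeat the primary analysis with pending coded as No, as a sensitivity analysis.

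The cost is one answer option, a few sentences in the analysis section, and slightly fewer evaluable respondents and cycles. The change has to be made before the survey opens, because the information cannot be recovered afterwards.

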Analysis: Descriptive statistics surrounding the ease of use on a 5-point likert (very easy to very difficult) will be analyzed on five different aspects of use. Specifically, the steps of using the Mosie Kit (collecting a sperm sample, drawing up the sample in the Mosie syringe, inserting the syringe, and depositing the sperm at or near the cervix) and overall ease of use will be examined. Additionally questions related to use such as comfort, ease and safety of the process, enjoyable and intuitiveness of use (able to use it without instructions) will allow the user to rate their experience from Strongly agree to strongly disagree (5 point scale). The data will be plotted and examined as part of the analysis.

Secondary Hypothesis 2: The participants were able to use the Mosie Kit as instructed using the instructions contained in the kit. The alternative hypothesis is that the participants were not able to use the kit using the instructions contained in the kit.

Analysis: Descriptive analysis of perceived overall success rate will be analyzed. Additionally, descriptive analysis of the frequency of each expected behavior related to use of the kit will be examined.

Secondary Hypothesis 3: The participants reported they used the kit as intended, specifically, using it within 24 hours of initial signs of ovulation and again 24-48 hours after ovulation was confirmed or expected. The alternative hypothesis is that the participants report they did not use the kit as intended with respect to timing (within 24 hours of initial signs of ovulation and again 24-48 hours post ovulation).

Analysis: Frequency rates related to timing of insemination at all reported cycles will be analyzed. The data will be reported in both total number of attempts at each time point as well as percentage of attempts at each time point in comparison with total cycles where the Mosie Kit was used. T-tests will also be used in this analysis. Additionally,

amount of time lying after insemination and position of lying will be analysed using descriptive statistics and correlations with pregnancy rate.

Secondary Hypothesis 4: Participants reported they perceived the Mosie Kit to be a safe way to conceive. The alternative hypothesis is that participants did not perceive the Mosie Kit to be a safe way to conceive.

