Appendix A: Online Survey Tool and Consent Form (Google Form)

This section shows what the Google Form will look like to the study participant. These are the questions the participant will be asked.

The first page of the study contains the consent form and the question that confirms the participant's agreement to participate.

There is skip logic for certain sections. For example, if the participant selects one cycle of using Mosie, the information related to cycles 2-6 will be skipped. If the participant selects that she is pregnant the questions related to the pregnancy will be asked, otherwise they will be skipped. If a donor was used, the questions related to producing a sperm sample will be skipped.

Note: Final language and questions might be tweaked or revised at any time to increase clarity.

MOSIE-001 © 2020 Mosie Baby Page 38

[figure not shown]
This is the inclusion/exclusion form.

If Participant selected to not participate in the study, he/she will see this screen next. If the participant said he/she is not 18 or older or has not used Mosie this screen will be displayed.

[figure not shown]

Qualifying participants will continue the survey on this page.

[figure not shown]

[figure not shown]
	ch of these diagnoses or issues do you believe are contributing to your rtility? *
	Not applicable
	PCOS
	Endometriosis
	Low AMH or low ovarian reserve
	Low Sperm count
	Sperm motility issues
	Erectile Dysfunction
	Performance issues or sexual anxiety, or inability to orgasm with partner
	Vaginismus or vulvodynia
	Tilted Uterus
	Multiple uterus/cervix
	Unexplained infertility
	Have only one functioning fallopian tube
П	Other:

[figure not shown]
No other method	is attempted			
Male/Female into	ercourse			
IVI or syringe oth	ner than Mosie			
IUI				
Femara				
Clomid				
IVF				
Cervical Cap				
Other:				
	None	1	2	3 or more
How many pregnancies have you had?	0	0	0	0
pregnancies	0	0	0	0
pregnancies have you had? How many live births have you had? How many pregnancies have you had that were	0	0	0	0
pregnancies have you had? How many live births have you had? How many pregnancies have you had	0	0	0	0

[figure not shown]

[figure not shown]
	0	1	2	3+
24-48 hours prior to ovulation	0	0	0	0
within 24 hours of ovulation	0	0	0	0
24-48 hours after ovulation	0	0	0	0
48+ hours after ovulation	0	0	0	0
Did you use Mosie fo Yes No	or another cy	cle?		

[figure not shown]

[figure not shown]

[figure not shown]

[figure not shown]

Mosie Kit Survey

* Required

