Mosie Kit Survey

* Required

Sperm Collection Process

[figure not shown]
How easy was it for you or your partner or known donor to deposit the sample into the cup? *

- O Very Difficult
- O Difficult
- O Easy
- O Very Easy

How stressful was the experience for your partner or donor to produce a semen sample at home (view point of the person providing the sperm)? *

[figure not shown]
- Not Stressful at all
- A Little Stressful
- Moderately Stressful
- O Very Stressful
- O Extremely Stressful

пач	e you or your partner had to produce a semen sample at a doctors office? *
0	Yes
0	No
To	what degree do you agree or disagree with the following statement:
Pro	ducing a sample at home was a lot less stressful than at the doctor's office.
0	Strongly Agree
0	Agree
0	Neutral
0	Disagree
0	Strongly DIsagree
Bac	k Next Page 14 o
Dac	k Next Page 14 o
er su	bmit passwords through Google Forms.
-	This content is neither created nor endorsed by Google. Report Abuse - Terms of Service - Privacy Policy

[figure not shown]
*	v would you rate your level of concern over the safety of using the Mosie Kit?
0	Not concerned at all
0	A little concerned
0	Somewhat concerned
0	Very concerned
0	Extremely concerned
	to help resolve the infection? (Please answer this on behalf of the personing Mosie to conceive.) *
usir	Account of the experience of the control of the con
O	Not Applicable: Did not have any vaginal infections
0	Nothing, it resolved on its own
_	
0	Douche or wash
0	Douche or wash Used over the counter (OTC) medications

olicable				
a or Yeast Infecti	on			
ginitis				
niniasis				
Next)	■ Page 15 of 20
words through Goo	gle Forms.			
	ginitis niniasis	ginitis	ginitis niniasis	ginitis niniasis Next

[figure not shown]

	I did not talk to my doctor
\circ	Strongly agree
\sim	
0	Agree
O	Neutral
0	Disagree
0	Strongly disagree
0000	I did not talk to my doctor Strongly agree Agree Neutral
0	Disagree
0	Strongly disagree
	our doctor had any concerns over using Mosie, would you please share them

	I would recommend Mosie to other people in my same situation. *
	O Strongly agree
	O Agree
	O Neutral
	O Disagree
	O Strongly disagree
	Overall how many stars would you give Mosie? Choose
	Back Next Page 16 of 20
Neve	er submit passwords through Google Forms.
	This content is neither created nor endorsed by Google. Report Abuse - Terms of Service - Privacy Policy
	Google Forms

[figure not shown]
Page 17 of 2

What is your ra	ce/ethnicity? *	

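### The ease-of-use row on collecting the sample in the cup has no 'not applicable' answer and no restricted denominator, so frozen sperm-bank users who may not have done the step count in its Secondary Hypothesis 1 result

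*Combined protocol and SAP*

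**What the plan says.** Section 9.1 (Secondary Hypothesis 1) states that "ease of use on a 5-point likert (very easy to very difficult) will be analyzed on five different aspects of use". It lists "the steps of using the Mosie Kit (collecting a sperm sample, drawing up the sample in the Mosie syringe" among them, followed by inserting the syringe, depositing the sperm, and overall ease. The planned analysis is descriptive.

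In Appendix A these five aspects form a grid on survey page 12 of 20. Its first row is "To collect the semen/sperm sample in the cup", and the visible columns are Very Easy, Easy, Neutral, Difficult and Very Difficult.

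Section 10.1.9.1 provides for "edit checks to ensure all questions are filled in". Section 7.2 says that incomplete surveys are discarded.

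Frozen bank sperm is expected in this population. A later checklist in Appendix A includes "Thawed out donor sperm from sperm bank", and the sample-type question, also printed after the grid, has an option that survives in clipped form as "rom a sperm bank (frozen".

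The introduction to Appendix A describes skip logic by section and says: "If a donor was used, the questions related to producing a sperm sample will be skipped". The Sperm Collection Process section that follows (survey page 14) asks: "How easy was it for you or your partner or known donor to deposit the sample into the cup".

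Section 4.1 plans to examine the secondary hypotheses by type of relationship as well as overall. Section 9.4.2 repeats this for all endpoints.

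**The concern.** The row on collecting the sample is meaningful only for someone who collected one, or whose partner or known donor did. The form itself treats the step as not applying to everyone: it skips sample-production questions for donor users, and it words the page 14 cup question for the respondent, partner or known donor, leaving out the sperm bank. The page 12 row has neither safeguard, and section 9.1 does not supply one at analysis.

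A bank user who reaches the row has no fitting answer. Whatever that person ticks enters the numerator or the denominator with the ratings of people who did the step. The row then no longer describes how easy the step was.

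The comparison by relationship type is more exposed. If bank sperm is used more in some relationship groups than in others, which is plausible but not quantified in the documents, a difference between groups would partly reflect who had no such step to rate. The survey is anonymous with no follow-up (section 4.3), so an unclear answer cannot be queried later.

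**Working it through.** **Order of the form.** The printed order in Appendix A is: the ease grid (page 12 of 20), the preparation checklist with the thawing item, the sample-type question, and the Sperm Collection Process section (page 14). A section-level skip triggered by sample type can remove page 14. It cannot remove a row already answered on page 12.

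**The plan's own precision figure.** Section 9.2 gives a 95% margin of 4.4 points with 500 surveys and 5 points with 384. The half-width is 1.96 × √(0.5 × 0.5 / n):
- n = 500: 1.96 × √(0.25/500) = 4.38 points
- n = 384: 1.96 × √(0.25/384) = 5.00 points

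Both figures reproduce and serve as the yardstick.

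**Effect on the row.** Let s be the share of bank users who did not do the step, p the true 'easy' rate among collectors, and q the rate at which those bank users tick an 'easy' answer. Then

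reported rate = (1 − s) × p + s × q.

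None of s, p and q is in the documents. I assume p = 80%, take s from 5% to 40%, and let q run over its whole range from 0 to 1. The last two columns give the sample size and half-width if the row is restricted to collectors, starting from 500 surveys.

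| s | reported, q = 0 | reported, q = 1 | n after restriction | half-width |
|---|---|---|---|---|
| 5% | 0.95 × 0.80 = 76% | 76% + 5% = 81% | 475 | 4.5 points |
| 10% | 0.90 × 0.80 = 72% | 72% + 10% = 82% | 450 | 4.6 points |
| 20% | 0.80 × 0.80 = 64% | 64% + 20% = 84% | 400 | 4.9 points |
| 30% | 0.70 × 0.80 = 56% | 56% + 30% = 86% | 350 | 5.2 points |
| 40% | 0.60 × 0.80 = 48% | 48% + 40% = 88% | 300 | 5.7 points |

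The largest downward shift is s × p. It exceeds the plan's 4.4-point margin once s is above 0.044/0.80 = 5.5%. At s = 5% it is 4 points, inside the margin. The largest upward shift is s × (1 − p), which is 2 points at s = 10%.

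**Effect on a comparison by relationship type.** Suppose p = 80% in two groups, with bank users 5% of one and 50% of the other (again assumed).
- All bank users tick Neutral: 0.95 × 0.80 = 76% against 0.50 × 0.80 = 40%.
- All tick an 'easy' answer: 76% + 5% = 81% against 40% + 50% = 90%.

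There is no true difference in either case, and the apparent one can go in either direction.

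**The case against.** The case on the other side has real substance.

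- *Compulsion is not proved.* The grid's stem and any required mark lie in a figure that is not shown, and some other items in Appendix A carry no asterisk. A reader might infer that bank users are forced to rate the row. The documents support only the general edit-check statement in section 10.1.9.1.
- *The skip trigger is not named.* Many earlier screens are missing figures, so an earlier question on sperm source cannot be ruled out. Even so, the skip is described for sections, and removal of a single grid row is unlikely.
- *The step may apply to some bank users.* The kit includes a cup (section 2.1), and no passage says whether thawed sperm passes through it. A reader might call these users' ratings invented. The documents do not support that; they support only that some may not have done the step.
- *No decision threshold is crossed.* The table falls below 50% at s = 40%, and a reader might infer that the hypothesis would flip. Section 9.1 sets no cut-off for Secondary Hypothesis 1; a majority is the wording of Secondary Hypothesis 5.
- *The page 14 scale is a separate matter.* That item has four answers in the opposite order. A reader might see a contradiction, but section 9.1 assigns the five-point grid to this hypothesis and does not name the page 14 item. Reversing a scale is a design preference.
- *The data can be repaired.* Sample type is collected, so the row can be restricted at analysis.

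What remains is that the visible grid has no opt-out and that section 9.1 does not state the restriction.

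**Conclusion.** The point holds as a minor one. As written, the collection row's denominator includes frozen sperm-bank users who may not have done the step, and neither the form nor section 9.1 takes them out. This can distort one descriptive row of five and its comparison by relationship type. The other three steps, the overall ease rating and the primary endpoint are not affected.

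The size cannot be determined from the documents. It rests on the share of bank users, the true 'easy' rate and what bank users tick, all of which are assumed above. It also rests on the row being required and on sample type not being asked earlier, neither of which can be confirmed while figures are missing.

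Separately, the donor skip and page 14 do not agree. Read literally, the skip removes every donor user, yet the page 14 cup question names known donors.

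**What to change.** - Add a column 'Not applicable - did not do this step' to the page 12 grid. State in section 9.1 that each step is analysed only in those who did it, with the denominator and the number not applicable reported. Appendix A already allows questions to be revised for clarity.
- For data collected without that column, restrict the collection row to respondents whose sample type is not frozen sperm-bank, and report that denominator. Apply the same restriction in the comparison by relationship type.
- Reconcile the donor skip in the introduction to Appendix A with the page 14 wording, so that known-donor users are not skipped from questions that name them.

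The cost is one column, one sentence in section 9.1 and one clarified skip rule. Precision for this row falls slightly: with 20% bank users the half-width goes from 4.4 to 4.9 points. The fallback restriction would also drop any bank user who did use the cup, which the new column would avoid.
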